1.1 Hypothesis

Hypothesis 1: Subjects in the Bright Light Treatment group will exhibit significant improvements as compared to Dim Light Treatment in fatigue, sleep and circadian activity rhythms.

Hypothesis 2: Subjects typed during baseline as having circadian dysrhythmia using actigraphy (circadian phase and amplitude abnormalities) will be significantly more likely to exhibit treatment responses.

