11.0 Data Management

11.1 Describe the data analysis plan, including any statistical procedures.

Hypothesis testing will be conducted using 2x2 ANOVAs for the first specific aim, with Logistic Regressions for the second specific aim (predicting treatment response and non-response) and with Linear and Logistic Regressions for the third specific aim (predicting illness severity and treatment response).

11.2 Provide a power analysis.

Response:

The primary outcome for sleep is the sleep efficiency score. Previous research has indicated that persons with satisfactory sleep have a sleep efficiency score exceeding 85, whereas persons reporting unsatisfactory sleep have a score at most 70, with both groups reporting a standard deviation of approximately 15. The estimated effect size from this study

is 1. The goal of this study is to improve sleep efficiency from an unsatisfactory level to a satisfactory level. Using a large effect size of .08 with a one-tailed significance of .025 and power of 80%, the required sample size for the two-group comparison is 26 per group for a total sample of 52.

11.3 Describe the steps that will be taken to secure the data (e.g., training, authorization of access, password protection, encryption, physical controls, certificates of confidentiality, and separation of identifiers and data) during storage, use, and transmission.

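### Aim 2 and the response part of aim 3 use logistic regression on an undefined binary response, although the outcomes are continuous scores measured before and after treatment

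*Combined protocol and SAP*

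**What the plan says.** Section 11.1 assigns 2x2 ANOVAs to aim 1. Aim 2 is to be tested "with Logistic Regressions for the second specific aim (predicting treatment response and non-response"; aim 3 "with Linear and Logistic Regressions for the third specific aim (predicting illness severity and treatment response". Hypothesis 2 (section 1.1) and the secondary endpoint (section 8.1) rest on the same idea: subjects with baseline circadian dysrhythmia "will be significantly more likely to exhibit treatment responses".

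No section defines a response. Section 11.2 comes nearest. It states "The primary outcome for sleep is the sleep efficiency score", and then gives two reference levels: "persons with satisfactory sleep have a sleep efficiency score exceeding 85" and "persons reporting unsatisfactory sleep have a score at most 70", "with both groups reporting a standard deviation of approximately 15". It adds: "The goal of this study is to improve sleep efficiency from an unsatisfactory level to a satisfactory level". It calls neither 85 nor 70 a response cut-off. The sleepiness cut-offs in section 12.7 are safety triggers.

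Sections 9.2, 9.4 and 9.5 list the measures: a 13-item FACIT fatigue score, insomnia and sleepiness scores, and actigraphy giving sleep efficiency, mesor, amplitude and acrophase. Section 9.2 has surveys and actigraphy done at baseline and again after treatment. Section 23.2 expects 50 recruited and 40 completing.

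**The concern.** There are two problems, and writing down a cut-off solves only one.

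First, the binary outcome is open. Response could be set on fatigue, sleep or circadian rhythm, as a level or as a change, at any cut. If that is settled after the data are seen, the test of Hypothesis 2 has no protection against a favourable choice.

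Second, the method cuts scores that the study already holds in full. With about 40 completers there is little information to spare, and a rule based on a level treats people just either side of the line as opposites while ignoring large changes that stay on one side. A pre-specified cut would remove the first problem and leave the second.

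**Working it through.** **Plan's own figure.** Section 11.2 gives 26 per group at one-sided 0.025 and 80% power. The printed effect size of .08 does not give 26: it needs about 2,453 per group. Read as 0.8, the normal formula gives n = 2(1.960 + 0.842)²/0.8² = 24.5, so 25, and the noncentral t gives 26. That reproduces the plan. It sizes the bright-versus-dim comparison only; aims 2 and 3 have no power calculation.

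**Inputs.** From section 11.2: levels 70 and 85, SD 15. From section 23.2: 40 completers, taken here as 20 per arm. Assumed: response means sleep efficiency above 85, the dim-light mean stays at 70, and the bright-light mean is 82 (70 + 0.8 × 15) or 85.

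**Loss from a split, normal scores.** Relative efficiency is φ(z)²/[p(1 − p)], where z is the distance of the cut from the mean in SDs and p is the proportion above it. This is a large-sample, small-effect measure.

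| Mean | z | p above cut | Efficiency | Loss |
|---|---|---|---|---|
| At the cut (85, or any median split) | 0 | 0.500 | 0.3989²/0.2500 = 0.637 | 36% |
| 82 | 0.2 | 0.421 | 0.3910²/0.2437 = 0.627 | 37% |
| 70 | 1 | 0.159 | 0.2420²/0.1335 = 0.439 | 56% |

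The first row applies to any normal score cut at its median, the most efficient cut, so it does not depend on 85.

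**Responders.** Among 40 completers: 20 × (0.159 + 0.421) = 11.6, or 20 × (0.159 + 0.500) = 13.2. If all 52 were analysed the range would be 15.1 to 17.1. If the dim-light mean rose to 75, it would be 13.5 to 15.0 of 40. Section 1.0 names four factors for aim 3 (time from treatment, de-prime, phase, amplitude). If they entered one model together, which section 11.1 does not say, there would be about 3 responders per predictor.

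**Illustration of power.** This is a two-group contrast with means 82 and 70, two-sided 0.05. It uses a t test on the score and a two-proportion z test on the split at 85.

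| Score distribution | Per group | Score | Split at 85 |
|---|---|---|---|
| Normal | 26 | 0.81 | 0.58 |
| Normal | 20 | 0.69 | 0.47 |
| Beta on 0-100 | 26 | 0.80 | about 0.80 |
| Beta on 0-100 | 20 | about 0.68 | about 0.68 |

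The beta rows keep the same means and SD, with sleep efficiency assumed to be a 0-100 percentage. Set k = m(1 − m)/s² − 1, a = mk and b = (1 − m)k. For m = 0.70, k = 0.21/0.0225 − 1 = 8.33, so a = 5.83 and b = 2.50. For m = 0.82, k = 0.1476/0.0225 − 1 = 5.56, so a = 4.56 and b = 1.00. The proportions above 85 are then 0.169 and 0.523, a gap of 0.35, against 0.421 − 0.159 = 0.26 under normality. The wider gap is why the loss disappears.

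**The case against.** The strongest reply is that this is a missing definition and no more: 85 is a reviewer's inference, and the losses depend on the assumed distribution. Much of that stands. Section 11.2 describes 85 and 70 as levels of two reference groups. The normal model is also strained: Normal(82, 15) puts 11.5% of people above 100 and Normal(85, 15) about 16%. With bounded scores the split at 85 can do as well as the score. The losses at 85 are therefore conditional.

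It is also right that the power contrast above is bright versus dim light. That is aim 1, which the plan already analyses by ANOVA. A reader might infer that the power of Hypothesis 2 falls from about 80% to about 58%. The documents do not support that: they give neither the prevalence of dysrhythmia nor an effect size for that contrast. A reader might also infer that all of aim 3 is dichotomised, but section 11.1 includes linear regression there, most naturally for illness severity.

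A third reply is that this is a pilot and aim 3 is described as preliminary. Hypothesis 2 and section 8.1 nevertheless state a significance claim, so the analysis behind it should be specified.

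What the objection does not remove is that response is undefined, that continuous baseline and post-treatment scores are available, and that a linear model using them needs no cut.

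**Conclusion.** The point holds for aim 2 and for the treatment-response part of aim 3. The plan names a binary analysis of an undefined response where continuous scores exist. The firm part is the open cut-off and the avoidable splitting of a score in a sample of about 40.

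The size is less certain. The loss is about 36% for a median split of a normal score. It is about 36-56% if 85 were the cut and scores were normal with SD 15, with about 12-13 responders among 40 if the dim-light mean stays at 70. It could be near zero at 85 if scores are bounded and skewed. No figure can be given for the power of Hypothesis 2. Aim 1 is not affected. The change should be made, but the defect is confined to the secondary and exploratory questions.

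**What to change.** In sections 8.1 and 11.1, make the outcome for aim 2 and the response part of aim 3 the continuous post-treatment score: sleep efficiency, FACIT fatigue and a named circadian measure. Analyse each by linear regression with the baseline score, treatment arm, the baseline predictor (for example dysrhythmia) and the arm-by-predictor interaction. The interaction is needed because the question is whether the predictor changes the benefit of bright light; without it the model shows only who ends with better scores. In about 40 people it will be imprecise, so report it as an estimate with a confidence interval.

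Reword Hypothesis 2 in section 1.1 to say that subjects with dysrhythmia show larger improvement with bright light. Keep a responder percentage as a descriptive summary only, with one outcome and one cut fixed in advance.

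The cost is wording in three sections and no new data. The small downside is that the main result becomes a mean difference and not a response rate; the descriptive percentage keeps the latter in view.

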1.0 Objectives

- Assess the effect of morning bright light versus dim light therapy (control) on fatigue and sleep continuity disturbance in lung cancer survivors.
- Predict efficacy to morning bright light therapy versus dim light therapy (control) on fatigue and sleep continuity disturbance in lung cancer survivors.
- Evaluate, in a preliminary way, the extent to which time from treatment (as a proxy iatrogenic effects), sleep homeostatic “de-prime” (mismatch between sleep opportunity and ability), and circadian factors (phase and amplitude) predict illness severity and treatment response.

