chemotherapy for lung cancer (n=50) had early (i.e. difficulty falling asleep) and middle (difficulty staying asleep) insomnia (Gooneratne, Dean et al. 2007, Dean, Finnell et al. 2010). Our most recent mixed method, longitudinal study with 4 measures over 6-months (n=29) found that 89% reported the occurrence of fatigue and 67% reported fatigue was persistent across treatment. In addition, poor sleepers (72%) had less activity, weaker rhythmicity and more phase delay compared to good sleepers before and during treatment for non-small cell lung cancer. Acrophase, where peak activity in a 24-hour period occurs, was significantly negatively related to FACT-L physical and functional subscales and total scores indicating later peak activity is related to poorer QOL. These findings support the occurrence of fatigue, sleep continuity disturbance and circadian activity rhythm disturbance in lung cancer survivors and support for the rationale for testing BLT.

2.3 Provide the scientific or scholarly background for, rationale for, and significance of the research based on the existing literature and how will it add to existing knowledge.

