8.0 Study Endpoints

8.1 *Describe the primary and secondary study endpoints.*

The primary endpoint is whether subjects have a significant improvement in self-reported fatigue, sleep and circadian rhythms with the bright light intervention as compared to the dim light intervention. The secondary endpoint is to determine whether pre-treatment subjects with circadian dysrhythmia (circadian phase and amplitude abnormalities) will be significantly more likely to exhibit treatment responses than those who were not identified as having circadian dysrhythmia.

8.2 *Describe any primary or secondary safety endpoints.*

Response: It is expected that some patients with stage I-III NSCLC may experience periods of low oxygenation during sleep that may be identified during screening with the ApneaLink. We added a letter of referral to give to patients who may wish to alert their Providers about this finding.

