12.0 Provisions to Monitor the Data and Ensure the Safety of Subjects

12.1 Describe the plan to periodically evaluate the data collected regarding both harms and benefits to determine whether subjects remain safe.

The PI will be responsible for ensuring data integrity and safety monitoring for human subjects and communicating any negative outcomes or any serious events to the IRBs and other offices/agencies. Because of the minimal to low risk associated with this protocol, the data safety and monitoring plan (DSMP) for this project involves close monitoring by the principal investigator (PI) and a safety officer, an Nurse Practitioner in the School of Nursing. The data safety monitoring team will ensure participant safety, ensure the validity and integrity of the data, monitor study progress, and make recommendations regarding appropriate protocol and operational changes which may have substantial effects upon the ultimate interpretation of the study. They will also be responsible for promptly report any serious adverse events to the Institutional Review Boards (IRB) at Roswell Park Cancer Institute, the VA Western New York Health Systems (VA WNYHS) and the University at Buffalo

Weekly reviews of participant accrual will be conducted by the PI during weekly research meetings. If participant accrual and/or retention drop below what is required for successful completion of this study, the PI will alert the statistician and strategies will be developed to overcome the identified problems. Records from subjects recruited during that week will also be scrutinized to insure that all participants are eligible for participation in the study. The PI and members of the research team will be monitoring developments in the literature and results of related studies that may have an impact on the safety of participants or on the ethics for the research study. Additionally, [name], a sleep research expert and consultant, will serve as a resource for new findings in the field and to assist with this clinical trial.

12.2 Describe what data are reviewed, including safety data, untoward events, and efficacy data.

Data review includes eligibility, referral for sleep apnea, referral for low oxygen during sleep, completion of data collection instruments, adherence to intervention, number of follow up phone calls accepted, and outcome measures of efficacy: fatigue, sleep and circadian activity rhythms. Daytime sleepiness will also be evaluated daily, but monitored weekly.

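### The Hypothesis 2 regression names neither a baseline value of the outcome nor a comparison by arm, so dysrhythmia can appear to predict response, in either direction, with no light effect

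*Combined protocol and SAP*

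**What the plan says.** Hypothesis 2 (section 1.1) reads: "Subjects typed during baseline as having circadian dysrhythmia using actigraphy (circadian phase and amplitude abnormalities) will be significantly more likely to exhibit treatment responses". Section 8.1 makes this the secondary endpoint and names the comparison group: dysrhythmic subjects "will be significantly more likely to exhibit treatment responses than those who were not identified as having circadian dysrhythmia". Section 11.1 supplies the method: "with Logistic Regressions for the second specific aim (predicting treatment response and non-response". It lists model families only. No covariate is named for any aim, and illness severity appears only as something aim 3 will predict.

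Two other places bear on the meaning of response. Objective 2 (section 1.0) is "Predict efficacy to morning bright light therapy versus dim light therapy (control) on fatigue and sleep continuity disturbance in lung cancer survivors", which limits the outcome to two domains and words the question as bright versus dim. The primary endpoint in 8.1 is wider: "significant improvement in self-reported fatigue, sleep and circadian rhythms with the bright light intervention". Section 12.2 likewise lists "outcome measures of efficacy: fatigue, sleep and circadian activity rhythms". Under 9.2, surveys and actigraphy are done at baseline and again after treatment.

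**The concern.** Subjects typed as dysrhythmic may simply start with worse sleep or fatigue. The team's own earlier work (section 2.2) points that way: "poor sleepers (72%) had less activity, weaker rhythmicity and more phase delay compared to good sleepers before and during treatment". If so, a response scored as improvement favours those who start worse, because an extreme baseline tends to drift back. A response scored as reaching a level counts against them, because part of their severity carries over. Both scorings are open: Hypothesis 1 speaks of improvement, while 11.2 sets the goal as moving sleep efficiency from an unsatisfactory to a satisfactory level.

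The secondary endpoint could therefore reach significance in a direction set by the choice of scoring. A link found in both arms together would also describe prognosis, not response to bright light, which is what Objective 2 asks about.

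**Working it through.** **The plan's own figure.** There is none for Hypothesis 2: no response rate, power or sample size is stated. The 26 per group in 11.2 is for sleep efficiency in aim 1. It follows from a standardised difference of 0.8 at one-sided 0.025 and 80% power (t-test 25.5, rounded up to 26). It is used here only for n.

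**Inputs.** n = 52 (9.1, 11.2) and 40 completers (23.2). Everything else is an assumption: normal outcome with SD 1; no light effect; dysrhythmia as a median split of an index correlated c = 0.3-0.5 with worse baseline; pre-post correlation ρ = 0.5-0.7; response as improvement of at least 0.5 SD, or a final value at least 0.5 SD above the mean; two-sided 5%, so 2.5% in each direction.

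**Step 1: size of the artefact.** A median split separates group means on the index by 2·√(2/π) = 1.596 SD. Baseline then differs by 1.596c, the final value by 1.596ρc, and the change by 1.596(1−ρ)c. The SD of change is √(2(1−ρ)): 1.00 at ρ = 0.5 and 0.775 at ρ = 0.7.

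| ρ | c | Gap in change (in SDs of change) | Gap in final level | Improved ≥0.5 SD, dysrhythmic vs other | Odds ratio |
|---|---|---|---|---|---|
| 0.5 | 0.3 | 0.24 (0.24) | 0.24 | 35.2% vs 26.6% | 1.50 |
| 0.5 | 0.5 | 0.40 (0.40) | 0.40 | 38.0% vs 23.6% | 1.98 |
| 0.7 | 0.3 | 0.14 (0.19) | 0.34 | 29.0% vs 23.0% | 1.37 |
| 0.7 | 0.5 | 0.24 (0.31) | 0.56 | 31.0% vs 21.0% | 1.69 |

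For example, (0.380/0.620)/(0.236/0.764) = 1.98. The true odds ratio for a light effect is 1. The gap in final level runs against the dysrhythmic group.

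**Step 2: false findings by simulation, n = 52, no baseline term.** Example cells: ρ = 0.5, c = 0.3 gives 8.3% (change) and 9.0% (level); ρ = 0.5, c = 0.5 gives 17.3% and 17.8%; ρ = 0.7, c = 0.5 gives 10.7% and 32.0%. Likelihood-ratio tests run slightly higher, up to 19% and 38%. Nearly all change-based findings favour Hypothesis 2, and nearly all level-based ones go against it. With 40 subjects, the low ends fall to about 5-7% and 6-9%. Adding the baseline value brings the total to 3-8%, depending on the test.

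**Step 3: link through stable traits only.** Dysrhythmia then correlates c with the outcome on both occasions, so the gap in change is zero and an unadjusted change score gives 5-6%. Baseline adjustment now misleads. The standardised coefficient of dysrhythmia given baseline is c(1−ρ)/(1−c²), which is 0.25/0.75 = 0.33 at c = ρ = 0.5 and 0.09/0.91 = 0.10 at c = 0.3, ρ = 0.7. In simulation this gave false links against Hypothesis 2 in about 13-31% of trials, fewer where ρ is high. A level-based response was wrong in up to about 65% unadjusted and about 15-30% adjusted.

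**Step 4: comparison by arm.** The interaction is the dysrhythmia gap in the bright arm minus the gap in the dim arm. With no light effect the two gaps are equal, so they cancel. Simulated rates were about 5-9% in every case above; adding baseline did not change this materially.

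**Step 5: precision of the interaction.** With 52/4 = 13 per cell and an assumed response rate of 0.3, the standard error of the log ratio of odds ratios is √(4/(13 × 0.21)) = 1.21. The 95% interval spans a factor of exp(1.96 × 1.21) ≈ 11 either way. With 10 per cell, the standard error is √(4/(10 × 0.21)) = 1.38 and the factor is about 15.

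**The case against.** Four points can be made for the plan.

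- Section 11.1 is silent on covariates for every aim; it does not exclude adjustment. This stands: a reader might infer that the plan rejects baseline adjustment, and the text does not say so. But with response and covariates both open, the result can turn on choices made after the data are seen.
- A reader might infer that response will be scored on the same actigraphy phase and amplitude that type the subject. With 52 subjects that would give false links in roughly 35-95% of trials. No passage says this will be done, and Objective 2 names only fatigue and sleep continuity. Sections 8.1 and 12.2 list rhythms as an efficacy outcome, so 8.1 does not rule it out, but those rates belong to a hypothetical reading and do not set the size of this point.
- The correlation of 0.3-0.5 is not in the documents. The work in 2.2 (n=29) compared good with poor sleepers before and during treatment, whereas this trial enrols survivors with sleep continuity disturbance. If 0.3-0.5 holds before selection, keeping only the worse half at baseline cuts it to 0.19-0.33, and at ρ = 0.5 the false-positive rates fall to 5.4-6.2% (change) and 6.1-8.8% (level). This narrows the point; it does not remove it, because the plan gives no numeric cut-off for selection.
- The dim arm is a built-in safeguard. That is right, but only if the arms are compared, and neither 8.1 nor 11.1 says that they will be. The interaction would also not by itself separate dysrhythmia from baseline severity if the benefit of light depends on severity; one such case tried (slope 0.4) stayed at 2.8-5.1%.

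**Conclusion.** The point holds in a bounded form. Run as written, the secondary analysis can yield a significant link with no light effect: about 8-19% of trials in favour of Hypothesis 2 (change) or 9-38% against (level) at n = 52, under the assumed correlations. These rates depend on those correlations and on the link acting through the baseline occasion. For a change score they return to near nominal if the link is through stable traits or is weakened by selection. Only the change-based artefact is regression to the mean; the level-based one is mainly carry-over of severity. Baseline adjustment alone is not a complete remedy. The comparison by arm kept close to its nominal rate throughout and matches the wording of Objective 2. This is a secondary endpoint in a pilot, so the plan should be amended, but the primary comparison is untouched.

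**What to change.** In 8.1 and 11.1:

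1. Score the aim 2 response on fatigue and sleep continuity only, as Objective 2 says, and not on the actigraphy rhythm measures used for typing. State the response definition and the dysrhythmia cut-off before the data are analysed.
2. Include the baseline value of the same outcome in the aim 2 model and in the aim 3 treatment-response models.
3. Make the dysrhythmia-by-arm interaction the test of Hypothesis 2. Report it with its confidence interval and label it exploratory, because power for an interaction at 40-52 patients is low.

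The cost is a few sentences and one degree of freedom each for baseline, arm and interaction. No new data are needed, since the baseline measures are already collected under 9.2. The real price is candour: a definite answer on Hypothesis 2 is not to be expected at this sample size.
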